AE=adverse event; AED=antiepileptic drug; ALP=alkaline phosphatase; ALT=alanine aminotransferase; AST=aspartate aminotransferase; BRIEF=Behavior Rating Inventory of Executive Function; BRIEF-P=Behavior Rating Inventory of Executive Function-Preschool Version; BRV=brivaracetam; CBCL=Child Behavior Checklist; C-SSRS=Columbia-Suicide Severity Rating Scale; DRC=daily record card; ECG=electrocardiogram; eCRF=electronic case report form; EEG=electroencephalogram; EV=Entry Visit; GGT=gamma-glutamyltransferase; IVRS=interactive voice response system; PedsQL=Pediatric Quality of Life Inventory; POS=partial-onset seizure; SAE=serious adverse event; ScrV=Screening Visit; TV=Titration Visit

^a The Screening Period will serve as the Baseline Period for directly enrolled subjects. Directly enrolled subjects will begin receiving BRV at TV1 after all

Table 5-3: Schedule of study assessments from the ScrV through the final TV (directly enrolled subjects only)

Period	Screening ^a	Up-Titration			
	Visit	Screening	Titration Visit 1	Titration Visit 2	Titration Visit 3
		(ScrV)	(TV1)	(TV2)	(TV3)
Assessment					

inclusion and exclusion criteria are met.

^b Vital sign measurements include blood pressure, pulse rate, and body temperature.

^c Height and head circumference will be recorded only at the ScrV.

^d A previous EEG documenting the diagnosis of POS must be available at the ScrV. If an EEG is not available at the ScrV, it must be scheduled during the Screening Period.

^e A neuro-imaging procedure (brain magnetic resonance imaging/brain computerized tomography scan [except in Germany]/ultrasounds or any other imaging test) should be performed if no report is available within the previous 2 years.

^f Seizure counts are collected in the subject's DRC on a daily basis.

^g A pharmacokinetic sample for determination of BRV plasma concentration should be obtained whenever a subject experiences an SAE.

^h Drug return includes study medication intake recording and accountability.

ⁱ The ScrV laboratory assessments for safety will include hematology, biochemistry (including hepatic monitoring of ALT, AST, ALP, total bilirubin, and GGT), urinalysis (for subjects for whom sample collection is feasible), endocrinology, and a urine pregnancy test at the site (for female subjects of childbearing potential). The TV laboratory assessments for safety will include only hepatic monitoring of ALT, AST, ALP, total bilirubin, and GGT.

Laboratory samples should be collected at TV2 only if the Investigator anticipates that it will be the final TV before the subject advances to the EV. The decision for treatment at TV1 will include the results of the laboratory sample collected at the ScrV.

^j The C-SSRS will be administered to subjects ≥ 6 years of age. The "Since Last Visit" version of the C-SSRS is to be used with the following exceptions: 1) the "Baseline/Screening" version of the C-SSRS should be used at the ScrV, and 2) if a subject turns 6 years of age during N01266, the "Already Enrolled" version of the C-SSRS should be completed at the first visit after the sixth birthday, and the "Since Last Visit" version of the C-SSRS should be completed at subsequent visits.

^k The version of the Achenbach CBCL (CBCL/1½-5 or CBCL/6-18) used at the ScrV should be in accordance with the subject's age at this visit.

^l The BRIEF-P should be used for subjects < 5 years of age at the ScrV. The BRIEF should be used for subjects ≥ 5 years of age at the ScrV.

^m The version of the PedsQL used should be consistent with the subject's age at the ScrV.

ⁿ This refers to any hospital stay that occurs during the study. Data recorded in the eCRF include the reason for the hospitalization, the admission ward, transfers, and length of stay.

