For LTFU subjects, the EV is the first study visit. For directly enrolled subjects, the EV is the visit at which subjects enter the Evaluation Period and occurs after subjects have completed the ScrV and at least 1 Titration Visit (TV). For subjects who continue in the study until it ends, the Evaluation Period will extend from the EV to the FV. For subjects who prematurely discontinue the study, the Evaluation Period will last from the EV until the EDV. Following the EDV, or following the FV for subjects who complete the study but do not continue BRV treatment, subjects will have their BRV dose reduced by a maximum of half the dose every week for a maximum of 4 weeks until a dose of 1mg/kg/day (50mg/day for subjects with

body weights >50kg) is reached. After 2 weeks free of study drug (Safety Period), subjects will complete the SV.

During the Evaluation Period, MEVs and FEVs will be performed alternatively every month during the first 3 months and every 3 months thereafter, with a YEV every 12 months. The sequence of these visits is presented in Section 5.3. Enrolled subjects who participate in EP0065 and then resume participation N01266 will maintain the visit schedule established for them in N01266 before participation in EP0065.

Both safety data and efficacy data (seizure data) will be collected during the study. Lists of the study assessments performed at each of the visits are presented in Section 5.2.

No formal interim analysis is planned; however, data may be reported prior to the completion of this study (see Section 12.8).

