End of study status			X ^v					X

AE=adverse event; AED=antiepileptic drug; ALP=alkaline phosphatase; ALT=alanine aminotransferase; AST=aspartate aminotransferase; Bayley-III=Bayley Scales of Infant and Toddler Development, Third Edition; BRIEF=Behavior Rating Inventory of Executive Function; BRIEF-P=Behavior Rating Inventory of Executive Function-Preschool Version; BRV=brivaracetam; CBCL=Child Behavior Checklist; C-SSRS=Columbia-Suicide Severity Rating Scale; DE=directly enrolled; DRC=daily record card; DTV=Down-Titration Visit; ECG=electrocardiogram; eCRF=electronic case report form; EDV=Early Discontinuation Visit; EEG=electroencephalogram; EV=Entry Visit; FEV= Full Evaluation Visit; FV=Final

Table 5–2: Schedule of all study assessments for the Evaluation, Down-Titration, and Safety (Drug-Free) Periods (all subjects)

Period	Evaluation						Down-Titration	Safety (Drug-Free)
	Minimal Evaluation Visit (MEV)	Full Evaluation Visit	Yearly Evaluation Visit/Final Visit	Unscheduled Visit	Early Discontinuation Visit	Down-Titration Visit		
Visit		(FEV)	(YEV/FV ^a)	(UV)	(EDV)	(DTV) ^b		
Assessment								

Visit; GGT=gamma-glutamyltransferase; IVRS=interactive voice response system; LTFU=long-term follow-up; M=Month; MEV=Minimal Evaluation Visit; PedsQL=Pediatric Quality of Life Inventory; SAE=serious adverse event; SV=Safety Visit; TV=Titration Visit; UV=Unscheduled Visit; V=Visit; YEV=Yearly Evaluation Visit

^a For subjects staying in the study until it ends, the same procedures as for a YEV should be performed at the subject's FV.

^b Visit should be scheduled at the end of the Down-Titration Period. The duration of the Down-Titration Period will depend on when the final dose of the study drug was taken during the Evaluation Period, with a maximum duration of 4 weeks.

^c Vital sign measurements include blood pressure, pulse rate, and body temperature.

^d An ECG has to be scheduled once a year at the YEV and at the EDV in the case of early discontinuation.

^e At the SV, ECGs, laboratory assessments for safety, and determination of phenytoin plasma concentration will be performed only if abnormal at the EDV.

^f EEG (for LTFU subjects only)

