- For subjects \geq 2 years of age at V5 who have typical absence seizures, an EEG of at least 1 hour that includes hyperventilation and intermittent photic stimulation must be performed at V5 and yearly thereafter. For subjects prematurely discontinuing from the study, an at least 1-hour EEG may be performed at the EDV at the Investigator's discretion.
- For subjects <2 years of age at V5, an EEG of at least 24 hours must be performed for efficacy assessment at V5 and yearly thereafter until subjects reach 2 years of age. For subjects prematurely discontinuing from the study, an at least 24-hour EEG may be performed at the EDV at the Investigator's discretion.

^g No DRC or study drug will typically be dispensed at the FV. However, for subjects who complete the study but do not continue BRV treatment, study drug for down-titration will be dispensed.

^h The assessment of seizure types will be done at 6-monthly intervals (at the FEV and the YEV) for subjects <2 years of age.

ⁱ For subjects enrolled in N01266 who volunteered to participate in EP0065 and then returned to N01266, changes to ongoing concomitant medications during EP0065 will be recorded in the N01266 eCRF.

^j For subjects enrolled in N01266 who volunteered to participate in EP0065 and then returned to N01266, ongoing AEs that stop during EP0065 will be recorded in the N01266 eCRF.

^k Drug return includes study medication intake recording and accountability.

^l Full laboratory assessments for safety include hematology, biochemistry (including hepatic monitoring of ALT, AST, ALP, total bilirubin, and GGT), and

Table 5–2: Schedule of all study assessments for the Evaluation, Down-Titration, and Safety (Drug-Free) Periods (all subjects)

Period	Evaluation						Down-Titration	Safety (Drug-Free)
	Minimal Evaluation Visit (MEV)	Full Evaluation Visit (FEV)	Yearly Evaluation Visit/Final Visit (YEV/FV ^a)	Unscheduled Visit (UV)	Early Discontinuation Visit (EDV)	Down-Titration Visit (DTV) ^b		
Assessment								

endocrinology for all subjects and urinalysis for subjects for whom sample collection is feasible as described in Section 9.2.1. Female subjects of childbearing potential should have a urine pregnancy test done at the site at all laboratory assessment visits. Endocrinology testing will be performed at the YEV/FV.

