7.2.3 Down-Titration Period

All subjects who prematurely discontinue the study should complete an EDV and have their BRV dose down titrated by a maximum of half the dose every week for a maximum of 4 weeks until a dose of 1mg/kg/day (50mg/day for subjects with body weights $>50\text{kg}$) is reached.

Equally, all subjects completing the study but switching to treatment other than BRV should have their BRV dose down titrated.

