8.10 Safety Visit (all subjects)

The SV will be performed after the subject has been free of study drug for 2 weeks (Safety Period).

- Physical examination
- Neurological examination
- Psychiatric and mental status
- Vital signs (blood pressure, pulse rate, and body temperature)
- Body weight, height, and head circumference
- ECG performed only if abnormal at the EDV
- DRC retrieved
- Seizure count
- Recording of medications
- Recording of procedures
- Recording of AEs
- Suicidality assessment (C-SSRS) (for subjects ≥ 6 years of age)
- IVRS call
- Laboratory assessments for safety (to be performed only if abnormal at the EDV)
 - Hematology
 - Biochemistry (including hepatic monitoring of ALT, AST, ALP, total bilirubin, and GGT)
 - Urinalysis (for subjects for whom sample collection is feasible)
 - Urine pregnancy test (see Section 9.2.1)
- Phenytoin plasma concentrations (if applicable) only if abnormal at the EDV
- Health care provider consultations not foreseen by the protocol
- Hospital stays
- End of study status

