8.11 Final Visit (all subjects)

Subjects who continue in the study until it ends should complete a FV.

- Childbearing potential
- Physical examination
- Neurological examination

- Psychiatric and mental status
- Vital signs (blood pressure, pulse rate, and body temperature)
- Body weight, height, and head circumference
- ECG
- EEG (for LTFU subjects only)
 - For subjects ≥ 2 years of age at V5 who have typical absence seizures, an EEG of at least 1 hour that includes hyperventilation and intermittent photic stimulation must be performed
 - For subjects < 2 years of age at V5, an EEG of at least 24 hours must be performed
- DRC retrieved
- Seizure count
- Recording of medications
- Recording of procedures
- Recording of AEs
- Suicidality assessment (C-SSRS) (for subjects ≥ 6 years of age)
- IVRS call
- Study drug returned
- Study drug compliance
- Laboratory assessments for safety
 - Hematology
 - Biochemistry (including hepatic monitoring of ALT, AST, ALP, total bilirubin, and GGT)
 - Urinalysis (for subjects for whom sample collection is feasible)
 - Urine pregnancy test (see Section 9.2.1)
 - Endocrinology
- BRV plasma concentrations
- Phenytoin plasma concentrations (if applicable)
- Bayley-III scales (for LTFU subjects enrolled in English-speaking countries and in countries where a validated translation is available, < 18 months of age at baseline of the core study, and < 42 months of age)
- Achenbach CBCL (see Section 10.3.3)
- BRIEF-P (≥ 2 years to < 5 years of age)/BRIEF (≥ 5 years of age) (see Section 9.3.8)

- PedsQL (see Section 10.3.5)
- Health care provider consultations not foreseen by the protocol
- Hospital stays
- End of study status
- Appointment for the next visit should be scheduled for the end of the 4-week Down-Titration Period (maximum) if BRV treatment is not continued after study completion (FV), and study drug for down-titration should be dispensed

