10.1 Efficacy assessments for seizure data based on DRC

At each visit, the subject/parent(s)/legal representative(s) will receive a DRC, which has to be filled in daily by the parent(s)/legal representative(s) or subject, if applicable, and returned at the next visit. No DRC will be dispensed at the SV or the FV.

The date and the number of epileptic seizures will be recorded on the DRC, as well as the type of seizure (according to individual description of seizures), occurrence of clusters, intake of concomitant AEDs, undesirable events with start and end dates, health care provider consultations not foreseen per protocol, and changes in concomitant medication, if applicable.

The written information will be discussed with the subject/parent(s)/legal representative(s) at each visit in order to ensure completeness and accuracy. As a result of the discussion, the Investigator will assess the seizures according to the ILAE codes and record the seizure types and frequency on the eCRF; he/she will also confirm the presence of AEs (if applicable). Concomitant medication changes, health care provider consultations not foreseen per protocol, and AEs will be reported by the Investigator on the specific pages of the eCRF.

The DRC will be considered as source documentation. The subject/parent(s)/legal representative(s) should be educated to complete the DRC on a daily basis (eg, when taking evening dose of BRV). Substantial noncompliance with diary completion (seizures recording) may result in subject discontinuation from the study at any time by the Investigator or the Sponsor.

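### Completers who stop BRV have no EDV, so the EDV-only trigger for repeat tests at the Safety Visit cannot apply to them, and they get no diary card for down-titration

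*Protocol*

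**What the plan says.** **Route off treatment.** Section 5.1 gives down-titration two starting points: "Following the EDV, or following the FV for subjects who complete the study but do not continue BRV treatment". Both lead, after two drug-free weeks, to the SV. Section 7.2.3 requires an EDV of subjects who discontinue prematurely and then adds: "Equally, all subjects completing the study but switching to treatment other than BRV should have their BRV dose down titrated". Section 8.11 has the FV schedule the DTV "if BRV treatment is not continued after study completion (FV), and study drug for down-titration should be dispensed".

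**SV repeat tests.** Table 5-2 footnote e reads: "At the SV, ECGs, laboratory assessments for safety, and determination of phenytoin plasma concentration will be performed only if abnormal at the EDV". Section 8.10 repeats the condition separately for the ECG, the laboratory tests and phenytoin; the laboratory item begins "Laboratory assessments for safety (to be performed only if abnormal at the EDV". Neither place names the FV.

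**Diary.** Section 10.1 states "No DRC will be dispensed at the SV or the FV" and also "The DRC will be considered as source documentation". Footnote g of Table 5-2 says "No DRC or study drug will typically be dispensed at the FV", and its exception for completers who stop BRV mentions study drug only. Section 8.11 lists retrieval of a DRC but not dispensing of one. Section 8.9 and Table 5-2 require DRC retrieval and a seizure count at the DTV for all subjects.

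**The concern.** The protocol provides an FV route into down-titration, but two rules that depend on the route were written as if every subject entering it came from an EDV.

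First, the SV repeat depends on a visit these subjects do not have. An abnormal last on-treatment ECG, laboratory or phenytoin result therefore has no scheduled drug-free repeat, whereas an early discontinuer with the same result gets one. The protocol gives no reason for the difference.

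Second, the DTV is told to collect a card that was not issued. The DRC is the source document for seizure counts, and under Section 10.1 it also records undesirable events with dates and changes in concomitant medication. Section 9.1.2 asks the investigator to review diary cards when looking for AEs. The card is missing while the dose is being reduced, when worsening seizures would be looked for. Early discontinuers receive a card at the EDV (Section 8.8).

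**Working it through.** The protocol states no figure to reproduce. The check compares the two routes visit by visit and then counts the days without a diary.

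| Step | Early discontinuer | Completer who stops BRV |
|---|---|---|
| Last on-treatment visit | EDV (8.8) | FV (8.11) |
| ECG, laboratory, phenytoin if applicable | Done | Done |
| Down-titration drug dispensed | Yes | Yes (8.11, footnote g) |
| DRC dispensed | Yes (8.8) | No (8.11, 10.1) |
| DTV: retrieve DRC, count seizures | Card exists | No card issued |
| DTV: dispense DRC for the drug-free period | Yes (8.9) | Yes (8.9) |
| SV: repeat ECG, laboratory, phenytoin | If abnormal at EDV | Condition cannot be met |

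**Repeat tests.** For a completer with abnormal FV results, 0 of the 3 conditional SV tests are scheduled, whatever the FV values were.

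**Diary gap, upper limit** (Sections 5.1 and 7.2.3):
- Down-titration lasts at most 4 weeks = 28 days; the drug-free period lasts 2 weeks = 14 days.
- Time from FV to SV is at most 28 + 14 = 42 days.
- Share without a diary = 28/42 = 67%. The remaining 14/42 = 33% is covered by the card dispensed at the DTV.

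**Diary gap at the fastest taper from the dose ceiling.** The dose may fall by at most half each week, down to 1 mg/kg/day, or 50 mg/day above 50 kg. Assumption: one week at each reduced dose, starting at the FV.
- By weight, from 5 mg/kg/day: 5 → 2.5 → 1.25 → 1.0 is 3 steps × 7 = 21 days; 21/(21 + 14) = 60%.
- Above 50 kg, from 200 mg/day: 200 → 100 → 50 is 2 steps × 7 = 14 days; 14/(14 + 14) = 50%.

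Subjects starting below the ceiling may need fewer steps.

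**Number affected.** The protocol does not give the number of completers who stop BRV or the proportion with an abnormal FV result, so no count of affected subjects can be derived.

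**The case against.** The strongest reply is that little depends on this.

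- **Analyses.** Section 10 evaluates seizure counts from EV to EDV or FV, and Section 12.3 presents safety tables over the Evaluation Period, which ends at the FV for these subjects. A diary kept after the FV enters no named efficacy variable. This stands.
- **Other follow-up.** An abnormal laboratory finding can be an AE (Section 9.1.1.1), and AEs are usually followed for 30 days after the drug is stopped, which outlasts the SV (Section 9.1.3). Section 9.2.2 requires initial abnormal hepatic tests to be repeated. The investigator judges the clinical significance of ECG abnormalities, and unscheduled visits are possible. SV examinations, vital signs and C-SSRS are unconditional. This also stands. It narrows the gap to abnormal results not reported as AEs or handled as possible liver injury, but it schedules no repeat of those.
- **Size of the group.** Approval, managed access and transfer to another BRV study (Section 5.1.1) all offer continued BRV, so few completers may stop. That is plausible but cannot be quantified from the protocol.
- **Diary wording.** Footnote g describes the usual practice rather than a ban, and Table 5-2 marks DRC dispensing at the YEV/FV. But the exception it spells out covers drug only, and Section 10.1 excludes a DRC at the FV without exception. Sites are not told to dispense a card.
- **Headline share.** The 67% applies to the longest permitted taper; faster tapers from the ceiling give 50% to 60%. All are shares of a post-treatment period of at most six weeks and measure days, not harm.

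**Conclusion.** Both gaps are present in the current text. For completers who stop BRV, the condition for the three SV repeat tests cannot be satisfied, and the DTV seizure count has no diary behind it from FV to DTV: at most 28 days, or 14 to 21 days at the fastest taper from the dose ceiling, assuming one week per step from the FV.

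The consequence is modest. It concerns one subgroup of unstated size, leaves AE, SAE and liver-injury safeguards in place, and does not touch Evaluation Period efficacy. It appears to be an omission rather than a deliberate choice. It should still be corrected: long-term safety is the primary objective, and otherwise similar subjects are followed differently only because of the visit at which they stop.

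**What to change.** 1. In Table 5-2 footnote e, and in all three conditional items of Section 8.10 (ECG, laboratory, phenytoin), change the trigger to *abnormal at the EDV or FV*.
2. In footnote g and Sections 8.11 and 10.1, provide for a DRC at the FV whenever down-titration drug is dispensed there.

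No visit is added. The cost is amendment wording, a few extra cards, and an occasional repeat test at a visit already scheduled.

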5.3 Visit sequence

Study visits are to be scheduled in the order presented in the following table:

Table 5–4: Visit sequence

Directly enrolled subjects		
	Visit	Type of visit
	ScrV	Screening
W1	TV1 ^a	TV
W2	TV2 ^a	TV
W3	TV3 ^a	TV
All subjects		
First year follow-up		
M0	V1	EV ^b
M1	V2	MEV
M2	V3	FEV
M3	V4	MEV ^c
M4	-	-
M5	-	-
M6	V5	FEV
M7	-	-
M8	-	-
M9	V6	MEV ^c
M10	-	-
M11	-	-
Second and subsequent years follow-up^d		
M12	V7	YEV
M15	V8	MEV

Table 5–4: Visit sequence

M18	V9	FEV
M21	V10	MEV
and every 3 months thereafter	V11, V12, etc	YEV, MEV, etc

BRV=brivaracetam; EV=Entry Visit; FEV=Full Evaluation Visit; LTFU=long-term follow-up; M=Month; MEV=Minimal Evaluation Visit; ScrV=Screening Visit; TV=Titration Visit; V=Visit; W=Week; YEV=Yearly Evaluation Visit

Note: Visits at W1, W2, W3, and M0 will occur 7 ± 2 days after the previous visit; visits at M1, M2, and M3 will occur 30 ± 7 days after the previous visit; visits at M6, M9, M12, M15, M18, M21, and every 3 months thereafter will occur 90 ± 15 days after the previous visit.

“-” denotes that no visit is scheduled in that month.

^a All directly enrolled subjects must participate in at least TV1, but may participate in fewer than 3 TVs as described in Section 7.2.1.

^b For directly enrolled subjects, the EV represents the point of entry into the Evaluation Period.

^c Hepatic monitoring tests only will be performed as described in Section 9.2.1.

^d Subsequent years will follow the same visit schedule.

5.4 Rationale for study design and selection of dose

N01266 will allow BRV long-term safety and tolerability data to be collected from pediatric subjects with epilepsy who will have participated in core studies and now have the opportunity to continue BRV treatment, and from directly enrolled subjects with POS. The safety and efficacy data collected in this study will support the applications for BRV indications in pediatric patients.

Each LTFU subject will begin treatment in N01266 at the individualized BRV dose he/she was receiving at the completion of the core study. Enrolled subjects who volunteer to participate in EP0065 will resume dosing in N01266 in accordance with the individualized dose they received at the completion of EP0065. Directly enrolled subjects will participate in up to 3 weeks of an Up-Titration Period. If a subject demonstrates, in the opinion of the Investigator, acceptable tolerability and seizure control on the same daily dose of BRV for 7 ± 2 days during the Up-Titration Period, the subject will be allowed to enter the Evaluation Period (subject must be able to tolerate the minimum dose of 1mg/kg/day; see Section 7.2).

A physiologically-based PK model (N01313) was developed to predict the doses to be tested in N01263. The same doses that were used for up-titration in N01263 will be used for the 3 consecutive weeks that comprise the Up-Titration Period of N01266. Based on the PK analyses performed on the plasma samples collected in N01263, the plasma concentrations approximating the concentrations for adults receiving BRV 200mg/day were not achieved by the dosing scheme initially included in N01266; as a result, it was recommended that the same doses are to be administered in all pediatric subgroups, ≥ 1 month to ≤ 16 years of age. For all subjects, the approximate doses to be administered are 0.5, 1, and 2mg/kg bid (1, 2, and 4mg/kg/day, respectively), with the daily doses not exceeding the maximums of 50mg/day, 100mg/day, and 200mg/day for Weeks 1, 2, and 3 of up-titration, respectively. The dose selection was based on the following observations:

- The PK of BRV is linear and of low variability in adults up to 1 order of magnitude above the therapeutic dose range.
- Efficacious doses in adults are expected to be from 50mg/day up to 200mg/day.
- In N01263, BRV was eliminated more rapidly in pediatric subjects than in adult subjects, resulting in a lower plasma concentration. Therefore, clearance of BRV was shown to be higher in pediatric subjects than in adult subjects.

Brivaracetam (tablet and oral solution) should be administered twice daily (bid) in 2 equally divided doses. All LTFU subjects must be able to tolerate the minimum dose specified in the core study to be eligible for entry into the Evaluation Period of N01266. All directly enrolled subjects must be able to tolerate at least 1mg/kg/day during the Up-Titration Period prior to entering the Evaluation Period of N01266, as indicated in Section 7.2.

The maximum allowable BRV dose in N01266 is 5.0mg/kg/day (2.5mg/kg bid), not to exceed a dose of 200mg/day. Subjects will receive oral solution or tablets, as appropriate.

The maximum BRV dose allowed in this study will be 200mg/day (100mg bid), which is the maximum allowed dose for those subjects dosed as adults.

5.5 Study conduct due to coronavirus (severe acute respiratory syndrome coronavirus-2) disease 2019

The following applies where normal study conduct is impacted by coronavirus (severe acute respiratory syndrome coronavirus-2 [SARS-CoV-2]) disease 2019 (COVID-19). The protocol visit schedule should be followed to the extent possible, considering the individual benefit-risk assessment by the Investigator. If necessary, remote visits may be conducted and the subjects or caregivers will be contacted by telephone or videoconference. Remote follow-up, at minimum with a telephone call after 3 months, must be done (preferably more frequently and as needed to follow-up on subject safety assessments).

If a subject needs to be discontinued and cannot come into the study site, then appropriate down-titration instructions will be provided, and a visit will be scheduled to perform safety assessments as soon as possible (see Section 7.2.3 for down-titration instructions).

In situations where a subject is unable to return to the study site, Investigators will assess and document the subject's safety via telephone contact. Based on information gathered from the telephone contact, Investigators will confirm whether the subject could continue the current study treatment based upon the outcome of the safety assessment. Subjects' agreement to implement this procedure should be obtained and documented prior to implementing any changes. Changes in the study treatment supply in this situation are described in Section 7.2.4.

Ad hoc subject contact may be warranted to understand the current health status of the subjects, follow up on AEs and inform them of any protective measures taken by the study site as a result of the COVID-19 pandemic (eg, any measures which may limit access to the site or may require additional actions by the subject prior to entry to the site).

Investigators and study coordinators may use discretion when determining the need to perform a home visit (eg, for safety laboratory parameters or PK samples).

If subjects are unable to return to the study site, protocol deviations will occur (even if the study visit is replaced by a home visit or remote visit) (Section 12.6). Investigators must carefully document the occurrence of these and any other deviations, clearly noting deviations which occurred during and in accordance to the COVID-19 pandemic.

If a subject visits another facility for a medical issue (or has to switch sites for some COVID-19-related reason), the Investigator should request contact with the physician providing care to provide a detailed explanation of the subject's condition and his/her participation in the study. Subjects or caregivers shall be reminded to completely collect and keep records of this visit.

In case laboratory assessments cannot be conducted via central laboratory vendor due to restricted site access or home visits by Investigators are not an option, local laboratory safety assessment may need to be conducted, in a format that allows the Investigator to receive and review these results and include as source documentation.

Deviations to data collection including inability to perform some assessments such as EEG, ECG or blood collection for safety laboratory assessments and PK, or alternative methods of assessment such as phone calls should be recorded in the source documentation and notated as "not done" in the electronic case report form (eCRF).

In cases where subjects cannot return to the study site, and it will not be possible to dispense a new DRC, subjects will be instructed to continue recording of seizures in a manner that is mutually agreed with the Investigator (eg, hand-written notes, taking notes on a smart device). Any recording of seizures in a manner outside of the study DRC must be carefully documented in the source medical records (copies or printouts of these recordings will be brought to and retained at site).

